### **Dermatology Life Quality Index (DLQI)**

The DLQI has been extensively used in clinical studies and has a large evidence base supporting reliability and validity. The DLQI is a self-administered, ten-question questionnaire used to assess the effect of different skin diseases on a subject's quality of life, overall health, and disability status. The questionnaire covers six domains including symptoms and feelings, daily activities, leisure, work and school, personal relationships and treatment and has a one week recall period. Each item is scored on a 4 point scale where a 0 score indicates "not relevant/not at all," and scores from 1 to 3 range from "a little," to "very much." Question 7 is a "yes"/"no" question where "yes" is scored as 3. If Question 7 is answered "no," scores range from 0 ("not at all") to 2 ("a lot").

### **Medical Outcome Short Form Health Survey (SF-36) Version 2 (Acute Form)**

The SF-36 is a widely used and extensively studied instrument to measure health-related quality of life among healthy subjects and patients with acute and chronic conditions. It consists of eight subscales that can be scored individually: Physical Functioning, Role-Physical, Bodily Pain, General Health, Vitality, Social Functioning, Role-Emotional, and Mental Health. Two overall summary scores, the Physical Component Summary (PCS) and the Mental Component Summary (MCS) also can be computed. The SF-36 has proven useful in monitoring general and specific populations, comparing the relative burden of different disease, differentiating the health benefits produced by different

treatments, and in screening individual subjects. The purpose of the SF-36 in this study is to assess the Health Related Quality of Life (HRQoL) of subjects. Given the acute nature of this disease, version 2, with a 1-week recall period, will be used in this study.

### **Patient Benefit Index (PBI)**

The PBI is a 25 item PRO instrument that assesses the benefit of psoriasis treatment. Patient relevant treatment needs and benefits are assessed through these 5 subscales: Reducing social impairment, reducing psychosocial impairments, reducing impairments due to therapy, reducing physical impairments, having confidence in healing. Treatment benefit is assessed using the PBI score ranging from 0 ("no benefit") to 4 ("maximal benefit").

### **Hospital Anxiety & Depression Scale (HADS)**

The HADS is a self-assessment scale which detects the presence and severity of anxiety and depression in the general population. It contains 14 items and is comprised of anxiety (7 items) and depression (7 items) subscales, which are scored separately and summed to give a total score. Item scores range from 0 (best) to 3 (worst) and total scores are categorized as normal (0 – 7), borderline abnormal (8 – 10) and abnormal (11 – 21). The HADS has been widely used in clinical trials in a variety of disease areas and has extensive evidence to support its acceptability, reliability and validity.

### **Patient's Global Assessment (PtGA)**

The PtGA is a PRO instrument to assess the patient's assessment of disease severity. This self-reported measure is used to assess disease activity using a 4-point scale where a higher score indicates higher level of disease activity. Disease activity is assessed from 0 ("complete disease control") to 3 ("uncontrolled disease").

### **European Quality of Life 5 Dimensions (EQ-5D)**

The EQ-5D is a standardized non-disease specific instrument for describing and valuing health-related quality of life. The EQ-5D consists of 5 dimensions: mobility, self-care,

usual activity, pain/discomfort, and anxiety/depression. Each dimension has 5 levels: no problem, slight problem, moderate problem, severe problem or unable to perform activity/extreme problem. It also contains a Visual Analogue Scale (VAS). Subjects are asked to indicate the level that describes their current level of function or experience for each dimension. As a measure of health status, it provides a descriptive profile and can be used to generate a single index value for health status, where full health is equal to 1 and death is equal to 0. The VAS records the subject's assessment of his/her own health along a vertical 20 cm line, which has health state scores between 0 and 100.

### **FUMADERM® INITIAL and FUMADERM® Subject Diary**

Subjects will be dispensed a paper diary at every visit, starting at the Week 0/Baseline visit and will be trained on how to complete the diary for FUMADERM® INITIAL and FUMADERM® (provided as study medication) dosing by site staff during the Week 0/Baseline visit. All subjects should complete their subject diary on a daily basis throughout the entire study. The diary will be reviewed by site personnel with the subject at each visit and collected at the Week 24/ET Visit.

The dosing records will be reviewed and verified for compliance at each visit by the site personnel at the study center and reinforced if necessary. All relevant dosing information will be captured into the eCRF by site personnel.

### **Study Drug Administration**

Refer to Section 5.5.1.

### **Monitoring for Hypersensitivity Reactions**

A hypersensitivity reaction is a clinical sign or symptom, or constellation of signs or symptoms, caused by an inappropriate and excessive immunologic reaction to study drug administration. A systemic hypersensitivity reaction is a hypersensitivity reaction that does not occur at the local site of study drug administration (e.g., not an injection site reaction). A serious systemic hypersensitivity reaction is a systemic hypersensitivity reaction that fulfills criteria for a serious adverse event.

Subjects should be closely monitored for signs and symptoms of hypersensitivity reactions for approximately 2 hours after the first dose administration (Week 0/Day 1) and 1 hour after all other doses of study drug (visits after Week 0/Day 1) in the patients randomized to risankizumab. Hypersensitivity reactions should be treated according to medical standards.

In the event of a suspected hypersensitivity reaction or other systemic post-dose reaction, a (PK/ADA) blood and urine sample will be collected once within 24 hours of the reaction.

In the event of a suspected systemic hypersensitivity reaction, a supplemental form that provides additional information is be completed by the investigator or designee.

### **5.3.2 Drug Concentration Measurements**

#### **5.3.2.1 Collection of Samples for Analysis**

##### **Blood Samples for Risankizumab Assay**

Blood samples, approximately 3 mL, for risankizumab assay will be collected by venipuncture into appropriately labeled collection tubes at the time points specified in [Appendix C](#). The timing of blood collection will take priority over all other scheduled study activities except for PROs, ECG and vital signs. Blood samples for the PK assay should be collected as closely as possible relative to the time of dosing and within 30 minutes prior to dosing. Date and exact time (to the nearest minute) of drug administration will be recorded on eCRFs. The time that each blood sample is collected will be recorded to the nearest minute in the source document.

A total of three samples will be collected per subject for pharmacokinetic analysis during the treatment and follow-up periods.

**Blood Samples for Risankizumab Anti-Drug Antibody (ADA) Assay:**

Blood samples, approximately 3 mL, for risankizumab ADA assay will be collected at the time points specified in [Appendix C](#). Blood samples for the ADA assay should be collected as closely as possible relative to the time of dosing and within 30 minutes prior to dosing. Date and exact time (to the nearest minute) of drug administration will be recorded on eCRFs. The time that each blood sample is collected will be recorded to the nearest minute in the source document.

A total of four samples will be collected per subject for ADA analysis during the treatment and follow-up periods.

**5.3.2.2 Handling/Processing of Samples**

Details for the handling and processing of the samples will be provided outside this protocol in the laboratory manual.

**5.3.2.3 Disposition of Samples**

The frozen serum samples for risankizumab concentration and risankizumab ADA assays will be packed and shipped from the study site to the Central Laboratory according to instructions in the central laboratory Lab Manual. An inventory of the samples included will accompany the package.

**5.3.2.4 Measurement Methods**

Serum concentrations of risankizumab and relative titers of risankizumab ADA will be determined using validated methods under the supervision of the Bioanalysis department at AbbVie. Any additional analytes may be analyzed using non-validated methods. Serum samples collected for risankizumab and risankizumab ADA analysis may be used for future assay development or validation activities.

The presence of ADA to risankizumab will be assessed via a tiered approach using a validated electrochemiluminescence assay (screening, confirmatory, and titration analysis

as appropriate). Samples that are confirmed positive may be further characterized in a validated neutralizing antibody (NAb) assay.

### **5.3.3 Efficacy Variables**

#### **5.3.3.1 Primary Variable**

The primary efficacy endpoint is the proportion of subjects with a  $\geq 90\%$  improvement in Psoriasis Area and Severity Index (PASI 90) at Week 24.

#### **5.3.3.2 Secondary Variables**

1. Proportion of subjects with a PASI 50/75/90/100 response at Weeks 4, 8, 12, 16, 20 and 24.
2. Change from baseline in PASI at Weeks 4, 8, 12, 16, 20 and 24.
3. Change from baseline in BSA affected by psoriasis at Weeks 4, 8, 12, 16, 20 and 24.
4. Proportion of subjects with a sPGA of 0 or 1 at Weeks 4, 8, 12, 16, 20 and 24.
5. Proportion of subjects with sPGA of 0 at Weeks 4, 8, 12, 16, 20 and 24.
6. Change from Baseline in PPASI Total Score at Weeks 16 and 24.
7. Change from Baseline in PSSI Total Score at Weeks 16 and 24.
8. Change from Baseline on the NAPPA-CLIN Total Score at Weeks 16 and 24.
9. Change from Baseline in Psoriasis Symptom Scale (PSS) total score at Weeks 16 and 24.
10. Proportion of subjects achieving PSS (0) at Weeks 16 and 24.
11. Change from Baseline in DLQI total score at Weeks 16 and 24.
12. Proportion of subject achieving DLQI (0, 1) at Weeks 16 and 24.
13. Change from Baseline in SF-36 PCS and MCS Scores at Weeks 16 and 24.
14. Change from Baseline in PBI at Weeks 16 and 24.

15. Change from Baseline on HADS at Weeks 16 and 24.
16. Change from Baseline on PtGA at Weeks 16 and 24.
17. Change from Baseline in EQ-5D-5L Index, EQ-5D Utility Index and VAS at Weeks 16 and 24.

The order of the secondary endpoints does not reflect a ranking.

#### **5.3.4 Safety Variables**

Safety evaluations include AE monitoring, physical examinations, vital sign measurements, and clinical laboratory testing (hematology, chemistry, and urinalysis) as a measure of safety and tolerability for the entire study duration.

#### **5.3.5 Pharmacokinetic Variables**

Risankizumab serum concentrations will be determined. Descriptive statistics will be calculated for each sampling time (study visit). The number and percentage of subjects with ADA will be calculated. Additional analyses combining pharmacokinetic and ADA data from this study and other studies may be conducted if appropriate.

### **5.4 Removal of Subjects from Therapy or Assessment**

#### **5.4.1 Discontinuation of Individual Subjects for Either Risankizumab or FUMADERM®**

A subject may withdraw from the study at any time. The Investigator may discontinue any subject's participation for any reason, including an adverse event, safety concerns or failure to comply with the protocol.

Whether randomized to risankizumab or to FUMADERM®, subjects will be withdrawn from the study immediately if any of the following occur:

1. Clinically significant abnormal laboratory results or adverse events, which rule out continuation of study drug, as determined by the Investigator and the AbbVie TA MD.
2. The Investigator believes it is in the best interest of the subject.
3. The subject requests withdrawal from the study.
4. Deviation from inclusion and exclusion criteria was noted after the subject started study drug, when continuation of the study drug would place the subject at risk as determined by the AbbVie TA MD.
5. Introduction of prohibited medications or dosages when continuation of the study drug would place the subject at risk as determined by the AbbVie TA MD.
6. Subject is non-compliant with TB prophylaxis (if applicable) or develops active TB at any time during the study.
7. The subject becomes pregnant while on study drug.
8. Subject has known malignancy, except for localized non-melanoma skin cancer. Discontinuation for carcinoma in-situ of the cervix is at the discretion of the Investigator.
9. Subject is significantly non-compliant with study procedures which would put the subject at risk for continued participation in the study in consultation with the AbbVie TA MD.
10. Occurrence of following hepatic test abnormalities considered by the investigator to be related to study drug:
  - Confirmed ALT or AST  $> 8 \times$  Upper Limit of Normal (ULN)
  - Confirmed ALT or AST  $> 5 \times$  ULN for more than 2 weeks
  - Confirmed ALT or AST  $> 3 \times$  ULN and (total bilirubin  $> 2 \times$  ULN)
  - Confirmed ALT or AST  $> 3 \times$  ULN with the appearance of fatigue, nausea, vomiting, right upper quadrant pain or tenderness, fever, rash, and/or eosinophilia ( $> 5\%$ )

If, during the course of study drug administration, the subject prematurely discontinues study drug use, the procedures outlined for the Early Termination Visit must be completed within 2 weeks after the decision to discontinue, and preferably prior to the initiation of another therapy. However, these procedures should not interfere with the initiation of any new treatments or therapeutic modalities that the Investigator feels are necessary to treat the subject's condition. Following discontinuation of the study drug, the subject will be treated in accordance with the Investigator's best clinical judgment.

A final telephone call will occur for all subjects who do not roll over into the extension study, approximately 15 weeks after the last dose of risankizumab and 7 weeks after the last dose of FUMADERM®, provided as study medication, to determine the status of any ongoing AEs/SAEs or the occurrence of any new AEs/SAEs.

All attempts must be made to determine the date of the last study drug dose and the primary reason for early termination. The information will be recorded on the appropriate eCRF page.

For subjects that are considered lost to follow-up, reasonable attempts must be made to obtain information on the final status of the subject. At a minimum, two phone calls must be made and one certified letter must be sent and documented in the subject's source documentation.

Subjects who discontinue the study prematurely will not be replaced.

Subjects are considered study completers if they have completed the Week 24 visit.

#### **5.4.1.1 Discontinuation of Subjects on FUMADERM®**

Subjects that are randomized to FUMADERM® INITIAL or FUMADERM® should be discontinued if any of the following occur:

1. A pronounced decrease in WBC count of > 50% between 2 visits or an absolute WBC count below 3,000/ $\mu$ l.

2. A lymphocyte count below 500/ $\mu$ l.
3. A lymphocyte count below 700/ $\mu$ l that persists 4 weeks after having reduced the dose of FUMADERM® INITIAL or FUMADERM® by half.
4. A Platelet count < 100 000/ $\mu$ l.
5. A diagnosis of progressive multifocal leukoencephalopathy.
6. An opportunistic infection, including but not limited to visceral herpes simplex, disseminated candidiasis, aspergillus colonization, acute pneumocystis carinii pneumonia or visceral CMV infection.
7. An increase in creatinine level above normal according to central laboratory normal range.
8. Severe rash/flush that does not resolve with continued treatment.
9. Major gastro-intestinal complaints that do not resolve with continued treatment in spite of dose reduction.

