### **5.3.1.1            Study Procedures**

Study procedures will be performed at the study visits as specified in [Appendix C](#). Study visits are scheduled at Week 0/Day 1, Weeks 4, 8, 12, 16, 20 and 24/ET. Study procedures are discussed in detail in this section, with the exception of drug concentration measurements and antibody measurements (discussed in Section [5.3.2](#)), study drug administration (discussed in Section [5.5.1](#)), and the collection of AE information (discussed in Section [6.1.1.1](#)). All study data will be recorded in source documents and on the appropriate eCRFs.

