**5.5                   Treatments****5.5.1               Treatments Administered**

Subjects randomized to risankizumab will receive SC injections of risankizumab in the form of [REDACTED] mg (150 mg total) pre-filled syringes at Weeks 0, 4 and 16.

Risankizumab will be administered as a SC injection in the abdomen, thighs, gluteal regions, or upper arms (contra-lateral to that used for pharmacokinetic (PK)/pharmacodynamics (PD) samples). The two injections done subsequently should be at least 2 cm apart and should not be close to a vein. The injection sites should avoid sites of psoriasis involvement as well as sites where the skin is tender, bruised, erythematous, or indurated and should be alternated to other areas for subsequent doses.

Subjects randomized to FUMADERM® will receive doses as noted in [Table 5](#).

FUMADERM® dose is increased with the intention of achieving PASI 90, if tolerability allows. The decision of a slow increase in FUMADERM® INITIAL or FUMADERM® dose or of a return to FUMADERM® INITIAL after initiation of FUMADERM® will be made by the investigator and the justifications for all deviations from the pre-specified dosing schedule of FUMADERM® will be documented in the eCRF. The maximum daily dose of FUMADERM® may not exceed 6 tablets per day. After the targeted efficacy on the psoriasis cutaneous lesions has been reached, an attempt should be made to reduce the dose of FUMADERM® to the individual maintenance dose. FUMADERM® INITIAL and FUMADERM® tablets must be swallowed without chewing with plenty of liquid during and immediately after meals. In general, care must be taken to ensure subjects drink sufficient liquids (i.e., 1½ to 2 liters) daily.

The dose of FUMADERM® INITIAL or FUMADERM® should be reduced if any of the following occur:

1.     A drop in lymphocyte count below 700/ $\mu$ l.
2.     A platelet count < 150 000/ $\mu$ l and  $\geq$  100 000/ $\mu$ l.

---

3. WBC count < 3 500/ $\mu$ l and  $\geq$  3 000/ $\mu$ l.
4. Gastrointestinal disorders, nausea, abdominal cramps, diarrhea.
5. Nervous system disorders (i.e., tiredness, dizziness or headache).

After dose reduction of FUMADERM®, the blood count should be monitored until it returns to normal.

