### **5.5.4                   Selection and Timing of Dose for Each Subject**

An IRT will be used to allocate study drug to subjects. At visits where study drug is to be administered/dispensed, study sites will be required to complete the study drug resupply module in the IRT to receive assigned study drug/kit numbers.

Risankizumab will be administered at the study site by authorized site personnel (e.g., study nurse) after all study procedures have been completed.

For subjects randomized to risankizumab, injections will be given in an open label fashion with each subject receiving █ injections of risankizumab (█ mg) at each dosing visit.

In exceptional cases of missed or delayed visits, risankizumab should not be administered within 14 days of the prior dose. There should be at least 14 days between two consecutive risankizumab administrations.

For subjects randomized to FUMADERM® INITIAL and FUMADERM®, drug will be provided to subjects for dosing at home as specified in Section [5.5.1](#).

Dose modifications or adjustments are not permitted for risankizumab. The dose modifications or adjustments for FUMADERM® INITIAL and FUMADERM® will be according to the investigator's instructions.

If one or several doses of FUMADERM® are missed, the patient should re-initiate the treatment with FUMADERM® according to the individualized dosing schedule. The subject should contact the site personnel or the investigator to confirm their dosing schedule. Any further adjustment of FUMADERM® dosing based on patient's individual efficacy and safety response is at the discretion of the investigator.

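### The stop for persistent lymphopenia presupposes a halved FUMADERM dose, but the dose-reduction rule at the same threshold sets no size

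*Protocol*

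**What the plan says.** Three places in the protocol govern a low lymphocyte count on FUMADERM.

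- **Reduction (5.5.1).** "The dose of FUMADERM® INITIAL or FUMADERM® should be reduced if any of the following occur", and the first trigger listed is "A drop in lymphocyte count below 700"/µl. No size or fraction is given. After a reduction, "the blood count should be monitored until it returns to normal".
- **Who sets the size (5.5.4).** "The dose modifications or adjustments for FUMADERM® INITIAL and FUMADERM® will be according to the investigator's instructions". The same section adds: "Any further adjustment of FUMADERM® dosing based on patient's individual efficacy and safety response is at the discretion of the investigator".
- **Stopping (5.4.1.1).** Item 2 stops FUMADERM below 500/µl, whatever was done to the dose. Item 3 stops it for a count below 700/µl that "persists 4 weeks after having reduced the dose of FUMADERM® INITIAL or FUMADERM® by half".

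Section 5.4.1 also has general withdrawal rules for both arms. Item 1 covers laboratory abnormalities that the investigator and the sponsor's medical director judge to preclude further treatment. Item 2 covers the investigator's view of the subject's interests. SAP 7.4 tabulates, as a protocol deviation, subjects who met a withdrawal criterion and were kept in the study.

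**The concern.** The two lymphocyte rules share a threshold and form one clinical sequence: reduce the dose, then stop if the count does not recover. The second step, however, depends on an action that the first does not require. A site can follow 5.5.1 exactly and still leave a subject outside the only rule written for persistent moderate lymphopenia.

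Protocol 3.2 lists lymphocytopenia among the common side effects of fumaric acid esters and mentions opportunistic infections, including isolated cases of progressive multifocal encephalopathy. Item 3 is the rule meant to act before the count reaches 500/µl without relying on judgement. If it applies to one subject and not to another with the same counts, only because a different number of tablets was removed, the safeguard is uneven across about 25 sites. The SAP deviation count would inherit that unevenness.

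**Working it through.** The plan gives no figure on this point, so the check compares the texts and adds simple tablet arithmetic.

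**Step 1. Is the size of the reduction fixed anywhere?** Section 5.5.1 item 1 gives none, and 5.5.4 assigns it to the investigator. Neither the protocol nor the SAP says that a reduction for lymphopenia must be by half, or what becomes of item 3 when it was smaller. Item 9 of 5.4.1.1 (gastro-intestinal complaints) refers to dose reduction without a size. Item 3 is the only criterion in that list that names one, so the words cannot be dismissed as filler.

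**Step 2. Which compliant reductions fall short of half?** Section 5.5.1 sets the ceiling: "The maximum daily dose of FUMADERM® may not exceed 6 tablets per day". Table 5 schedules 6 tablets for Weeks 8-24. For a daily dose of t tablets cut to k, the reduction is (t − k)/t.

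| Dose t | Cuts below half, to k (size) | Cuts of half or more, to k (size) |
|---|---|---|
| 6 | 5 (17%), 4 (33%) | 3 (50%), 2 (67%), 1 (83%) |
| 5 | 4 (20%), 3 (40%) | 2 (60%), 1 (80%) |
| 4 | 3 (25%) | 2 (50%), 1 (75%) |
| 3 | 2 (33%) | 1 (67%) |
| 2 | none | 1 (50%) |

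At the 6-tablet dose, 2 of the 5 whole-tablet cuts to a non-zero dose are below half. Both satisfy 5.5.1.

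**Step 3. Follow two subjects with the same course.** Both take 6 tablets, fall into the 500-699/µl range, are reduced, and stay in that range for more than 4 weeks.

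- *Cut from 6 to 3 (50%).* Item 3 is met, so the subject should be discontinued.
- *Cut from 6 to 4 (33%).* Item 2 is not met, because the count is not below 500/µl. Item 3 is not met as worded, because the dose was not halved. Items 1 and 4-9 concern other findings and apply only if those occur. Section 5.4.1 items 1-2 can act, but by judgement.

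**Step 4. Consequence for the SAP.** If the second subject continues, one site may read item 3 literally and report no deviation under SAP 7.4. Another may read it as covering any reduction and report that a withdrawal criterion was ignored. The documents do not settle which is right.

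**Step 5. Size.** Protocol 3.0 reports lymphopenia in 10.6% of FUMADERM subjects in the cited study. Assuming the same rate here, 0.106 × 55 = 5.8, or about 6 subjects. That figure is for lymphopenia of any grade. The group at issue must also stay at 500-699/µl, have been reduced by less than half, not be halved later, and not be withdrawn on other grounds. None of these shares is given.

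**The case against.** The strongest reply is that the two rules can be read together: reduce the dose, and stop if halving has failed. On that reading, differing outcomes depend on whether halving was tried, which is how a stepped rule works. FUMADERM dosing is also said to follow the label (5.6.1, 5.6.4), which may guide sites on the size of a reduction and is not available here. This is a possible reading, but 5.5.1 does not state it and 5.5.4 leaves the size open.

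Four stronger readings are tempting and are not supported.

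- *A reader might infer that such a subject can never be stopped, or that no rule acts above 500/µl.* That is wrong. Item 3 applies if the dose is later halved, other FUMADERM criteria such as the white-cell rule may apply, and 5.4.1 items 1-2 are available throughout.
- *A reader might infer that the rule fails because odd tablet counts cannot be halved.* Scheduled on-treatment blood counts fall at Weeks 4, 8, 12, 16, 20 and 24, where Table 5 gives 2 tablets (Week 4) or 6 (Week 8 onward), all even. Odd doses arise only with individual titration, early visits or unscheduled counts. There are two strengths (30 mg and 120 mg), and 5.5.1 allows a return to INITIAL.
- *A reader might infer that the visit schedule cannot show 4-week persistence.* No laboratory turnaround is stated, counts are taken every 4 weeks, visits have a ±4-day window (5.1), and repeat testing is required (5.3.1.1 after Table 3; 5.5.1).
- *A reader might infer that the efficacy and safety results shift.* A subject who stops without a Week 24 PASI is generally imputed as a non-responder, but no calculation shows a shift, and the number affected is unknown.

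**Conclusion.** The concern holds as a conflict between the reduction rule and the persistence rule. A subject reduced by less than half has been managed as 5.5.1 asks, yet lies outside 5.4.1.1 item 3 as worded for as long as the count stays at 500-699/µl and the dose is not halved. The backstops narrow this gap. They do not close it, because within that range the remaining general rules are discretionary.

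This is more than missing detail, since exact compliance can bypass a stated safety stop. It is also limited: it touches one item of one list in one arm, probably in few subjects, and leaves the primary analysis as specified. The conclusion rests on the literal wording of the three sections and on taking a reduction by half to mean at least half. It does not rest on the 10.6% figure, which only indicates scale.

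**What to change.** Sections 5.4.1.1 item 3, 5.5.1 item 1 and 5.5.4 must be reconciled so that the reduction rule and the persistence rule refer to the same reduction, and so that it is clear which subjects the persistence rule covers. The content is for the sponsor's medical team to decide; no dose, step or stopping threshold is proposed here. Once the rule is clear, the SAP 7.4 deviation category can be applied uniformly without a change to the SAP.

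The cost is two or three sentences in an amendment and a letter to sites. No new data collection is needed for classification: 5.3.1.1 already has dosing information entered in the eCRF, and 5.5.1 already has departures from the pre-specified FUMADERM schedule justified there.
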